8.5.5 Pharmacokinetics

8.5.5.1 All Participants

Serum concentrations of BMS-986036 will be derived from trough (predose) blood samples collected from each participant before the administration of BMS-986036 dosing at each visit. Participants will be instructed to not administer study medication on the days of clinic visits until the trough PK sample has been collected.

[figure not shown]

[figure not shown]
Table 9 Timing of Pharmacokinetic and Electrocardiogram Assessments

[figure not shown]
Study Day	Event	Time Postdose (sample window)	Pharmacokinetic Sample	Electrocardiogram
Assessments Associated with the Day 1 Visit				
Day 1 (Day of Week 1 dose)	Predose	0 h	X	X
Day 1	Dose			
Day 8 (Day of Week 2 dose)	Predose	0 h	X	
Day 8	Dose			
Assessments Associated with the Week 24 Visit				
Day 169 (Day of Week 25 dose)	Predose	0 h	X	X
Day 169	Dose			
Day 176 (Day of Week 26 dose)	Predose	0 h	X	
Day 176	Dose			

[figure not shown]
Pharmacokinetic samples should be taken after the electrocardiogram assessments are performed at times where both pharmacokinetic samples and electrocardiograms are to be collected.

Day 1 is defined as the day of administration of the first dose of study medication.

BMS-986036 concentrations will be evaluated by a central laboratory. Further details of sample collection, processing, submission and storage are provided in the Study Laboratory Manual.

9. STATISTICAL CONSIDERATIONS

9.1 Sample Size Determination

The primary efficacy endpoint is the proportion of participants who achieve a ≥ 1 -stage improvement (as defined by NASH CRN Fibrosis Score) in fibrosis without worsening of NASH or NASH improvement (as defined by NAFLD Activity Score) with no worsening of fibrosis at Week 24, as determined by liver biopsy.

It is planned to randomize approximately 160 participants to 1 of the 4 treatment groups (approximately 40 participants per group), BMS-986036 10 mg QW, BMS-986036 20 mg QW, BMS-986036 40 mg QW or matching placebo QW in a 1:1:1:1 ratio.

A Cochran-Armitage trend test of proportions, with an estimated response rate of 15% for the primary endpoint for placebo and response rates for BMS-986036 10 mg QW, BMS-986036 20 mg QW, and BMS-986036 40 mg QW of 20%, 30%, and 40%, respectively, would provide at least 80% power at a 1-sided $\alpha = 0.05$ (based on the original sample size estimate of 160 participants). The final sample size was 197 participants (see [Section 6.2](#)).

9.2 Populations for Analyses

The following populations are defined for analysis purposes:

Population	Description
Enrolled	All participants who sign informed consent.
Randomized	All participants who are randomized, analyzed as per randomized treatment.
Modified intent-to-treat (mITT)	All participants who are randomized and receive at least 1 dose of study medication, analyzed according to randomized treatment. All primary efficacy analyses will be conducted using this population.
As treated (Safety)	All participants who are randomized and receive at least 1 dose of study medication, analyzed according to treatment actually received. This population will be essentially same as the mITT unless a participant received an incorrect treatment, i.e., a treatment different from what he/she was randomized to. All safety analyses will be conducted using this population.

9.3 Stratification

Randomization of participants will be stratified by country (non-Japan versus Japan). Participants in countries other than Japan will be stratified at randomization according to T2DM status (yes versus no) and NAS (≤ 5 versus > 5). Japanese participants will not be further stratified.

9.4 Endpoints

9.4.1 Efficacy Endpoints

9.4.1.1 Primary Efficacy Endpoint

The primary efficacy endpoint is the proportion of participants who achieve a ≥ 1 -stage improvement (as defined by NASH CRN Fibrosis Score) in fibrosis without worsening of NASH or NASH improvement (as defined by NAFLD Activity Score) with no worsening of fibrosis (as defined by NASH CRN Fibrosis Score) at Week 24 as determined by liver biopsy.

For this protocol, improvement in fibrosis is defined as a decrease of fibrosis by ≥ 1 point, as determined by the NASH CRN Fibrosis Score. Worsening of fibrosis is defined as an increase of fibrosis by ≥ 1 point, as determined by the NASH CRN Fibrosis Score.

Worsening of NASH is defined as an increase of the NAFLD Activity Score (NAS) by ≥ 1 point. NASH improvement is defined as a decrease of NAS by ≥ 2 points (with contribution from > 1 NAS component) (see [Section 8.5.1.1](#)).

9.4.1.2 Secondary Efficacy Endpoints

Secondary efficacy endpoints are as follows:

- Proportion of participants with NASH CRN Fibrosis Score improvement at Week 24
- Proportion of participants with Ishak Score improvement at Week 24
- Proportion of participants with a decrease in CPA at Week 24
- Proportion of participants with NASH resolution (NAS component of ballooning 0 and inflammation 0-1) without worsening of fibrosis (as defined by NASH CRN Fibrosis Score) at Week 24
- Proportion of participants with NASH resolution (NAS component of ballooning 0 and inflammation 0-1) at Week 24
- Proportion of participants with NASH improvement (reduction of NAFLD Activity Score by ≥ 2 points with contribution from > 1 NAS component) without worsening of fibrosis at Week 24
- Proportion of participants who achieve a ≥ 1 -stage improvement (as defined by NASH CRN Fibrosis Score) in fibrosis without worsening of NASH
- Proportion of participants with NASH improvement (reduction of NAFLD Activity Score by ≥ 2 points with contribution from > 1 NAS component) at Week 24
- Proportion of participants with progression to cirrhosis (as defined by NASH CRN Fibrosis Score) at Week 24

9.4.2 Safety Endpoints

Safety will be assessed by the following:

- Incidence and frequency of treatment-emergent AEs and SAEs
- ECGs at Week 24, and Week 48
- Vital signs at each visit
- Physical examinations (full or abbreviated as shown in [Section 8.5.3](#)) at each visit through Week 52/PTFU

- Laboratory evaluations at each visit through Week 52/PTFU
- BMD as measured by DXA at Week 48 (or ET, if applicable), and 6 months (1 month is defined as 4 calendar weeks) after the Week 52/PTFU Visit
- Anti-BMS-986036 antibodies at each visit with follow-up for up to 14 months (1 month is defined as 4 calendar weeks) after the Week 52/PTFU Visit as described in [Section 8.5.3.6](#)
- Anti-FGF21 antibodies at each visit with follow-up for up to 14 months (1 month is defined as 4 calendar weeks) after the Week 52/PTFU Visit as described in [Section 8.5.3.6](#)

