Hepatic magnetic resonance imaging (MRI)			X		X	X	Assessment window \pm 7 days. See Section 8.5.1.3 . For participants prematurely discontinuing study medication prior to Week 24, MRI should be conducted at the ET Visit if the date of discontinuation is more than 4 weeks from the date of the previous MRI. For participants prematurely discontinuing study medication after Week 24, MRI should be conducted at the ET Visit if the date of discontinuation is more than 8 weeks from the date of the previous MRI

Procedure/Assessment	Double-Blind Treatment						Follow-Up
	Day 1 Visit	After Day 1, up to Week 24 Visits every 4 weeks (\pm 5 days)	Week 24 Visit (\pm 5 days)	After Week 24, up to Week 48 Visits every 8 weeks (\pm 5 days)	Week 48 Visit (\pm 5 days)	Early Termination (ET) (if applicable)	
Weight for body mass index (BMI) calculation	X		X		X	X	X
Waist circumference	X		X		X	X	
3-Level EuroQol 5 Dimension (EQ-5D-3L) quality-of-life questionnaire	X		X		X	X	
36-Question Short Form Health Survey (SF-36) Version 2	X		X		X	X	

Procedure/Assessment	Double-Blind Treatment						Follow-Up
	Day 1 Visit	After Day 1, up to Week 24 Visits every 4 weeks (± 5 days)	Week 24 Visit (± 5 days)	After Week 24, up to Week 48 Visits every 8 weeks (± 5 days)	Week 48 Visit (± 5 days)	Early Termination (ET) (if applicable)	
Chronic Liver Disease Questionnaire-Nonalcoholic Fatty Liver Disease (CLDQ-NAFLD)	X		X		X	X	See Section 8.5.1.6
Clinical Safety Assessments							
Adverse events	X	X	X	X	X	X	See Section 8.5.3.1 and Appendix 8
Concomitant medications	X	X	X	X	X	X	See Section 8.3.7
12-lead electrocardiogram	X		X		X	X	If a participant has a QTcF >480 msec at an on-treatment visit, it should be confirmed by repeat ECG 30-60 minutes after the initial ECG. If the QTcF is confirmed to be >480 msec, the medical monitor should be contacted. See Section 8.5.3.5 and Table 9 in Section 8.5.5
Vital signs	X	X	X	X	X	X	See Section 8.5.3.4
Full physical examination			X		X	X	See Section 8.5.3.3
Abbreviated physical examination	X	X		X			See Section 8.5.3.3

Procedure/Assessment	Double-Blind Treatment						Follow-Up
	Day 1 Visit	After Day 1, up to Week 24 Visits every 4 weeks (± 5 days)	Week 24 Visit (± 5 days)	After Week 24, up to Week 48 Visits every 8 weeks (± 5 days)	Week 48 Visit (± 5 days)	Early Termination (ET) (if applicable)	

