Participants will be stratified at randomization by country (Non-Japan versus Japan). Participants in countries other than Japan will be stratified at randomization according to

T2DM status (yes versus no) and NAS (≤ 5 versus > 5). Japanese participants will not be further stratified.

[figure not shown]
The number of participants with NAS of < 4 will not exceed 15% of the total number of randomized participants.

Randomized participants will receive their assigned double-blind study medication for a total of 48 weekly doses. The treatment will be administered by SC injection of 2 pre-filled syringes of study medication in the abdomen according to their assigned treatment arm (see [Section 8.4.2](#)). During the Double-Blind Treatment Period ([Table 2](#) in [Section 1](#)), participants will be evaluated for safety and efficacy every 4 weeks (± 5 days) through Week 24 and every 8 weeks (± 5 days) after Week 24 through Week 48.

Participants will then return at Week 52 (± 5 days) for a PTFU Visit. Participants who discontinue study medication earlier than Week 48 will have an Early Termination (ET) Visit at the time of study medication discontinuation and will return for a PTFU Visit 4 weeks (± 5 days) after the ET Visit.

Participants will return 6 months (± 14 days) (1 month is defined as 4 calendar weeks) after the Week 52/PTFU Visit for DXA to assess BMD and for collection of samples for potential immunogenicity testing as well as serum and plasma biomarker samples (see [Table 3](#) in [Section 1](#)). Participants may need to return at 9 months, 12 months, and 14 months (± 14 days) (1 month is defined as 4 calendar weeks) after the Week 52/PTFU Visit if required for immunogenicity testing, as described in [Section 8.5.3.6](#) (see [Table 3](#) in [Section 1](#)).

[figure not shown]
Figure 1 Study Design Schematic – Screening to Week 52/PTFU

ET = early termination; PTFU = Post-Treatment Follow-Up; QW = once weekly

^a For participants who discontinue study medication prematurely, liver biopsy will be performed at ET if the participant has completed at least Week 20 and has not had a Week 24 biopsy. If a participant discontinues study participation prior to Week 20, they should consider having a liver biopsy at ET.

Figure 2 Study Schematic – Bone Mineral Density and Immunogenicity Follow-Up Visits After the Week 52/PTFU Visit (visit windows \pm 14 days) (1 month is defined as 4 calendar weeks)

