4.3.2 Electrocardiograms (ECG)

- Absolute and change from baseline values at Week 24, and Week 48
- Post-baseline abnormalities defined by the below categories:
 - Absolute QTcF (QT interval corrected using Fridericia's formula) prolongation
 - >450 msec
 - >480 msec
 - >500 msec
 - Change from baseline in QTcF Interval at Week 24, and Week 48
 - >30 msec
 - >60 msec

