6.2.3 ECGs, Vital Signs, and Physical Examinations

Based on the safety population, vital sign and 12-lead ECG parameters will be summarized by visit, treatment group, and pooled BMS-986036. All vital signs and ECG results will be listed.

ECG results will be summarized for continuous variables and will be presented for the absolute result and change from baseline. QTcF (QT interval corrected using Fridericia's formula) values will be presented with the implementation of corrections (i.e., Fridericia's) as defined in ICH Guidelines E14 by the following categories:

Absolute QTcF interval prolongation:

- o QTcF interval > 450ms
- o QTcF interval > 480ms
- o QTcF interval > 500ms

Change from baseline in QTcF interval:

- o QTcF interval increases from baseline >30ms
- o QTcF interval increases from baseline >60ms.

Physical examination results and other safety data will be listed.

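### SAP 4.3.2 ties the QTcF-increase counts to Weeks 24 and 48, SAP 6.2.3 does not, and no rule places the early-termination ECG in the safety tables

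*Protocol*

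**What the plan says.** **Collection.** In protocol Table 2 the ECG row ("12-lead electrocardiogram X X X X") has its four marks under Day 1, Week 24, Week 48 and ET. None falls at the four-weekly visits before Week 24. Protocol 8.1 fixes when ET happens: "Participants who discontinue study medication earlier than Week 48 will have an Early Termination (ET) Visit at the time of study medication discontinuation". The post-treatment follow-up visit comes 4 weeks later.

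**Endpoint definitions.** The ECG item in protocol 9.4.2 reads "ECGs at Week 24, and Week 48". In the same list, the bone-density item does name early termination: "BMD as measured by DXA at Week 48 (or ET, if applicable". SAP 4.3.2 defines the ECG endpoint as "Absolute and change from baseline values at Week 24, and Week 48", and heads the >30 and >60 msec categories "Change from baseline in QTcF Interval at Week 24, and Week 48". The absolute categories (>450, >480, >500 msec) stand under post-baseline abnormalities with no visit named.

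**Analysis section.** SAP 6.2.3 says that vital signs and "12-lead ECG parameters will be summarized by visit, treatment group, and pooled BMS-986036". It repeats both sets of QTcF categories without naming any week, and it lists all ECG results. It does not mention ET.

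**The concern.** An ECG taken as a participant leaves treatment is often the one a safety reviewer most wants to see, and here it is already collected. If the programmer follows SAP 4.3.2, that ECG does not enter the QTcF-increase counts. If the programmer follows SAP 6.2.3, it may enter, perhaps as a separate ET row. The same data could therefore give two different tables, and the choice would be made at programming.

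At stake is whether the between-arm counts of QTcF increases cover everyone with a post-baseline ECG, or only those who reached Week 24. No primary or secondary efficacy result is affected.

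**Working it through.** The plan states no figure on this point, so there is none to reproduce. The check is a comparison of the sections, followed by a scale under an assumption.

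**Step 1. Visits named for each ECG quantity**

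| Quantity | Protocol 9.4.2 | SAP 4.3.2 | SAP 6.2.3 |
|---|---|---|---|
| ECG values and changes | Weeks 24, 48 | Weeks 24, 48 | By visit, none named |
| QTcF increase >30, >60 msec | Not mentioned | Weeks 24, 48 | No week limit |
| Absolute QTcF >450, >480, >500 msec | Not mentioned | Post-baseline, no visit limit | No week limit |
| Individual results | Not mentioned | Not mentioned | All listed |

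The conflict lies in the first two rows, between the two SAP sections. The protocol item gives no QTcF category, so the limit on QTcF increases comes from SAP 4.3.2 alone.

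**Step 2. Does another rule settle where ET goes?**

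- SAP 8.3 tabulates assessments at the planned visit recorded in the database. It does not map ET to Week 24 or Week 48.
- SAP 6.4 gives ET its own summary for non-biopsy endpoints, but it governs the exploratory analyses, not safety ECGs.
- SAP 8.1 defines a change in the maximum post-baseline value (highest post-baseline value minus baseline). The SAP text does not assign it to ECGs.
- Protocol 9.5.3 says only that ECG abnormalities, where there are any, will be summarized.

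None of these places an ET ECG in the safety tables.

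**Step 3. Three participants under the literal text of SAP 4.3.2**

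- Completes treatment: the Week 24 and Week 48 ECGs count.
- Stops before Week 24: the visible schedule gives one post-baseline ECG, at ET, and it does not count towards the increases.
- Stops between Weeks 24 and 48: Week 24 counts; the later ET ECG does not.

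One caution applies to the second case. The follow-up column of Table 2 is not fully readable in the public copy: the urinalysis row shows no follow-up mark although Table 8 schedules that test through Week 52. Parts of the section around Table 9 are also removed. An unseen follow-up ECG is possible, but it too would fall outside Weeks 24 and 48.

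**Step 4. Scale**

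Let d be the proportion stopping before Week 24. The documents do not give it, so 5% to 20% is assumed. The number with no ECG in the increase counts is d × 197, or d × 197 / 4 per arm if spread evenly:

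- d = 5%: 0.05 × 197 = 9.85, about 10 (2.5 per arm)
- d = 10%: 0.10 × 197 = 19.7, about 20 (4.9 per arm)
- d = 15%: 0.15 × 197 = 29.55, about 30 (7.4 per arm)
- d = 20%: 0.20 × 197 = 39.4, about 39 (9.9 per arm)

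Those stopping between Weeks 24 and 48 are additional, but each keeps a Week 24 value.

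**The case against.** The strongest reply is that exclusion is not settled. SAP 6.2.3 is the analysis section, ET is a visit column with an ECG mark, and a by-visit table could well carry an ET row. That is right, and it is why the point is a conflict between two SAP sections and not a proven omission. It does not remove the conflict, because SAP 4.3.2 is explicit about the two weeks and SAP 6.2.3 does not name ET.

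A second reply is that a real signal would still surface. Every ECG is listed. Protocol 8.5.3.1 has significant ECG worsening recorded as an adverse event, and SAP 6.2.1 tabulates events leading to discontinuation by arm. This stands as reassurance. But a listing is not a count by arm, and a rise of more than 30 msec need not be judged an adverse event.

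A third is that the maximum-value derivation already exists in SAP 8.1, and that the table shells, kept in a separate document, may use it. That is possible. The SAP text does not say so, and by-visit rows alone do not show how many participants ever crossed a threshold.

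A reader might also infer more than the documents support:

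- *That ET ECGs are lost from the whole ECG endpoint.* They are not. The absolute QTcF categories have no visit limit in SAP 4.3.2.
- *That the omission depends on outcome or arm and so understates harm.* Protocol 8.3.9.1 does require stopping for some adverse events, but its list has no QTcF criterion. Protocol 8.5.3.5 sends a confirmed on-treatment value above 480 msec to the medical monitor without requiring a stop. QT prolongation is not among the events of special interest in 8.5.3.7, and 6.1.1 reports no adverse cardiovascular effects in animals. Selective stopping is a possibility, not a finding.
- *That a percentage under-count can be given.* It would need QTcF exceedance rates for completers and early stoppers, and the documents give neither.

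**Conclusion.** The point holds as an unreconciled difference between SAP 4.3.2 and SAP 6.2.3, with no safety rule for ET ECGs. Under the literal text of SAP 4.3.2, the ECG values, changes and >30/>60 msec increase counts omit scheduled ECGs that the trial collects, including the only visible post-baseline one for a participant who stops before Week 24. The early stoppers affected would number about 10 to 39 of 197 if 5% to 20% stop before Week 24. That range is an assumption, and the effect on the counts themselves cannot be sized or signed. This is a modest improvement to a Phase 2 safety table, worth making because it needs no new data.

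**What to change.** - In SAP 4.3.2 and 6.2.3, state that the QTcF categories, absolute and increase, use all post-baseline ECGs including ET. Because SAP 8.1 keeps unscheduled measurements out of the summaries, say also whether repeat ECGs count.
- Add one row for each arm and for pooled BMS-986036 that counts each participant once, on the largest post-baseline QTcF and on the largest increase. The SAP 8.1 definition of change in the maximum post-baseline value supplies the derivation.
- Use as denominator the participants with at least one post-baseline ECG and, for the increases, a baseline ECG as well.
- In protocol 9.4.2, give the ECG item the same ET qualifier that the bone-density item carries.

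The cost is a few lines of SAP wording, the matching qualifier in the protocol, and one extra table row. The ECGs are already scheduled and listed.

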9.4.3 Pharmacokinetic Endpoints

- Trough (predose) BMS-986036 concentrations from samples collected at each visit
-

9.4.4 Exploratory Endpoints

- Quantitative measurements of fibrosis and fat on biopsy
 - Assessment of NASH CRN Fibrosis Score at Week 24
 - Assessment of Ishak Fibrosis Score at Week 24
 - Assessment of fibrosis using digital pathology at Week 24
 - Assessment of CPA at Week 24
 - Assessment of fat in stained tissue by morphometry at Week 24
 - Assessment of alpha smooth muscle actin at Week 24
- Assessment of NAS at Week 24
- Assessment of NASH using digital pathology
- Hepatic fat fraction as measured using MRI-PDFF at Week 24 and Week 48
- Noninvasive measures of fibrosis and/or cirrhosis
 - Liver stiffness as determined by MRE at Week 24 and Week 48
 - Noninvasive scores of hepatic fibrosis (APRI, FIB-4, ELF, and NAFLD Fibrosis Score) at Week 24 and Week 48
- Metabolic assessments at Week 24 and Week 48
 - Physical assessments (body weight, waist circumference, and BMI)
 - Serum lipids (LDL, HDL, and TGs)
 - Plasma glucose
 - Plasma insulin
 - Hemoglobin A1c
- Patient-reported outcomes at Week 24 and Week 48
 - EQ-5D-3L questionnaire
 - SF-36 questionnaire
 - CDLQ-NAFLD questionnaire

- Exploratory biomarkers
 - Transaminases
 - ALT normalization (ALT \leq ULN) at Week 24 and Week 48
 - AST normalization (AST \leq ULN) at Week 24 and Week 48
 - ALT at each visit through Week 52/PTFU
 - AST at each visit through Week 52/PTFU
 - Change from Baseline (Day 1 predose) ALT levels at each visit through Week 52/PTFU Visit
 - Change from Baseline (Day 1 predose) AST levels at each visit through Week 52/PTFU Visit
 - PRO-C3
 - Assessment of PRO-C3 levels at each visit through Week 52/PTFU
 - Change from Baseline (Day 1 predose) in PRO-C3 levels at each visit through Week 52/PTFU Visit
 - Assessment of adiponectin at each visit through Week 52/PTFU

9.5 Statistical Analyses

A full Statistical Analysis Plan (SAP) will be developed that will provide more details for the statistical analysis methods to be used. The SAP will be finalized before database lock for the Week 24 data analysis and will provide detailed specifications of the analysis of all efficacy endpoints and safety. The SAP will also provide more details on the definition of analysis populations to be used in the analyses and procedures for accounting for missing data. The following provides a summary of planned statistical analyses of the primary and secondary endpoints; exploratory analyses will be described in the SAP.

9.5.1 Demographic and Baseline Characteristics

A description of the participant population will be included in a statistical output report, including subgroups of age, gender and race.

Demographic and Baseline characteristics will be summarized using frequency distributions and descriptive statistics using the Randomized Participants and modified intent-to-treat (mITT) populations. No statistical analyses will be performed to compare treatment groups at Baseline.

9.5.2 Efficacy Analyses

Efficacy analyses will be performed using the modified intent-to-treat (mITT) population unless otherwise specified below.

